7.2 Follow-up

All patients will be monitored with clinic visits, labs, and serial imaging (CT or MR scans and PET/CT if possible), and other tests as needed.

Patients deemed resectable at any time during follow-up may proceed to surgery. These patients will be withdrawn from the protocol and followed for survival.

Patients will have consultations in the first year every three months following study treatment as defined in the Study Calendar (Section 14); a follow up at 4-6 weeks is optional and may be done to assess subject's resectability, or if clinically indicated by study PIs or patient's treating physician.

For years 2 and 3, follow-up is recommended every 6 months, or until death or study withdrawal (due to progression, patient withdrawal, or noncompliance as defined in Section 7.5 Criteria for Removal from Study). Follow up intervals may be more frequent as indicated clinically. In the event of intolerable toxicity from mFFX, subjects will still be followed per protocol although chemotherapy may be altered or discontinued, the decisions of which will be left to the treating Medical Oncologist. Visits should include:

- Consultation with physical examination
- Labs: CBC, CMP, CA199. CEA and research bloods are optional.
- Scans: CT or MR and PET/CT if possible (PET/CT is recommended at 3 month follow-up visit but is not required)
- QOL (Quality of Life) Assessment with EORTC QLQ C-30 / PAN26 survey
- Adverse Event (AE) evaluation
- Concomitant Medications: PPIs and pain medications as applicable
- Other tests as appropriate.

Patients who remain on-study will be followed until death and cause of death should be obtained when possible.

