7.4 Duration of Follow Up

Patients will remain enrolled on this protocol until there is evidence that their disease has progressed either locally or distantly; or until study withdrawal for any reason. These patients will be followed for survival.

Progression may be determined by imaging or clinical criteria, i.e., increasing ascites and cachexia. We estimate that most patients will remain a subject in this study for approximately one year. Schedule of follow-up will be as according to the Study Calendar in Section 14.

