7.5 Criteria for Removal from Study

Patients will be withdrawn from the study for any of the following reasons:

- disease progression (as defined in Section 15.1.2 Disease Parameters)
- patient withdrawal
- pregnancy
- patient noncompliance, or failure of the patient to follow instructions of the study staff
- protocol director decides that continuing participation could be harmful to the patient
- treatment needed for patient that is not allowed in the study
- patient is deemed resectable and proceeds to surgery
- study cancellation
- other administrative reasons
- unanticipated circumstances.

Patients will continue mFFX on-study until one of these endpoints; in the event of intolerable toxicity from mFFX, subjects will still be followed per protocol although chemotherapy may be altered or discontinued, the decisions of which will be left to the treating Medical Oncologist.

Patients withdrawn from the study will be followed for overall survival only.

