17.4 Plan of Analysis

Demographic and clinical characteristics of patients and the characteristics of treated lesions (volume, location, and modality) will be summarized by means, medians, standard deviations, ranges and proportions as applicable.

Time to event outcomes (overall survival, metastasis free survival, and progression free survival) will be summarized using Kaplan-Meier curves and medians with 95% confidence intervals calculated using Greenwood's formula. Cox proportional hazards models will be used to compare treatment groups and to assess risk factors (e.g. biologic markers and PET volume). The effect of site will be tested in the Cox models; the effect of whether or not the patients received Leucovorin will also be tested in the Cox models. The level of response (and other categorical outcomes) will be tabulated at each follow-up interval. Logistic regression and Cox models will be used to assess the proportion with a response category depending upon the level of censoring prior to the annual visit.

The measurements of the volume of the pancreatic tumors based upon CT and PET-CT scans will be compared using paired t-tests or Wilcoxon signed-rank tests as appropriate. The agreement between pancreatic tumor measurements will be compared among the three institutions using correlation coefficients, percentage agreement, and inter-correlation coefficients.

Quality of life outcomes will be assessed at each time interval and compared using the recommended guidelines from the module. Differences in QOL for the two treatment groups will be explored using a repeated measures model in order to account for the within-patient correlation. Special interest will be placed on exploring the aspects of QOL which are known to be impacted by SBRT.

At this time all research on biomarkers for disease progression is exploratory. The goal is to potentially identify biomarkers that are associated with disease progression. Should any biomarkers be identified, their impact on the time to event outcomes will be summarized using Kaplan Meier curves and they will be tested using Cox proportional hazards models.

Quality of life at each interval will be calculated and compared using the recommended guidelines from the module (available by E-mail: [contact]). Efficacy outcomes with repeated measurements over time (e.g. quality of life) will be analyzed using a generalized estimating equation (GEE) approach to account for within-patient

correlation.

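### Quality of life is assigned to GEE with no missing-data handling, although collection appears to stop at progression and the design expects that sooner in the control arm

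*Combined protocol and SAP*

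**What the plan says.** Section 17.4 makes two statements about the QOL model. One is general: "Differences in QOL for the two treatment groups will be explored using a repeated measures model". The other is specific: outcomes measured repeatedly, with QOL given as the example, "will be analyzed using a generalized estimating equation (GEE) approach to account for within-patient" correlation. Neither gives a working correlation, weighting, a missing-data assumption, a sensitivity analysis or a way of handling death.

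On data collection, section 7.2 lists this among the follow-up visit items: "QOL (Quality of Life) Assessment with EORTC QLQ C-30 / PAN26 survey". It recommends visits in years 2 and 3 every 6 months, "or until death or study withdrawal (due to progression, patient withdrawal, or noncompliance" as set out in section 7.5). Section 7.4 says: "Patients will remain enrolled on this protocol until there is evidence that their disease has progressed either locally or distantly", or until withdrawal for any other reason. Section 7.5 lists among the reasons for removal "disease progression (as defined in Section 15.1.2 Disease Parameters"), and also surgery in patients found resectable. It then states: "Patients withdrawn from the study will be followed for overall survival only".

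No sentence says outright that questionnaires stop at progression. The study calendar in section 14 shows QOL at visits in year 2 and later, without a footnote on progression. But nothing provides for QOL after withdrawal, so the three sections read together imply that it stops.

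**The concern.** GEE without weighting is not generally valid when the chance of dropping out depends on earlier scores. Here the main cause of dropout would be progression, which the design expects sooner in the control arm. If patients with poor scores progress earlier, those still reporting are a selected, healthier group, and more so in the control arm. The comparison could then show a QOL deficit for SBRT that does not exist, or hide a benefit.

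This matters because section 2.3 says that QOL will be compared directly between the arms and gives palliation as part of the main potential benefit of SBRT. With the GEE details left open, the choices that govern the size of any bias could also be made after the data are seen.

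**Working it through.** **Inputs.** Sections 17.3.2 and 17.5.2: median PFS 6 (control) and 10.2 months (SBRT), exponential, 86 per arm, 60 months accrual, at least 12 months follow-up, two-sided 0.05, 91% power, 160 expected events (83 + 77). The plan states no QOL figures.

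**1. Reproduce the plan's figures.** Let λ = ln 2 / median. Events per arm = 86 × [1 − (e^(−12λ) − e^(−72λ)) / (60λ)].

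- Control, λ = 0.1155: 86 × [1 − (0.2500 − 0.0002)/6.931] = 82.9.
- SBRT, λ = 0.0680: 86 × [1 − (0.4424 − 0.0075)/4.077] = 76.8.
- Total 159.7, against 160 stated.

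Hazard ratio = 6/10.2 = 0.588. Schoenfeld power: Φ(√160/2 × 0.5306 − 1.96) = Φ(1.396) = 91.9%. Freedman power: Φ(√160 × 0.2593 − 1.96) = Φ(1.319) = 90.6%. The stated 91% is reproduced, so the medians can be used with confidence.

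**2. Share still able to report QOL**, 0.5^(t/median):

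| Month | Control | SBRT |
|---|---|---|
| 3 | 71% | 82% |
| 6 | 50% | 67% |
| 9 | 35% | 54% |
| 12 | 25% (about 22 of 86) | 44% (38 of 86) |
| 24 | 6% | 20% |

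**3. Bias under assumed dropout mechanisms.** The simulation used 150,000 patients per arm, visits at 0, 3, 6, 9 and 12 months, and reporting that stops at progression, with retention calibrated to step 2. Assumptions not in the documents: baseline 70 on a 0–100 scale, between-patient SD 15, residual SD 12, mean slope −0.5 and slope SD 1.0 per month, and dropout strength as a log hazard ratio per SD. Visits are timed from randomization, whereas section 14 times them from completion of study treatment. Underlying trajectories are equal in the two arms. The reference is the month-12 mean over all patients, whether or not they have progressed. Entries are bias in SBRT minus control; Monte Carlo error is about 0.1–0.2.

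| Dropout depends on | Strength | GEE independence | GEE exchangeable | Likelihood model |
|---|---|---|---|---|
| nothing | – | 0.11 | 0.05 | 0.03 |
| last observed score | 0.3 | −2.18 | −0.30 | −0.05 |
| last observed score | 0.6 | −3.77 | −0.45 | 0.14 |
| last observed score | 1.0 | −4.74 | −0.65 | 0.17 |
| current unobserved score | 0.3 | −2.67 | −1.22 | −1.11 |
| current unobserved score | 0.6 | −4.68 | −2.34 | −2.29 |
| current unobserved score | 1.0 | −5.85 | −3.23 | −3.72 |
| latent slope | 0.3 | −1.65 | −1.45 | −1.35 |
| latent slope | 0.6 | −3.04 | −2.68 | −2.56 |
| latent slope | 1.0 | −3.78 | −3.22 | −3.10 |
| nothing; QOL falls 10 at progression | – | −1.94 | −1.91 | −1.92 |
| nothing; QOL falls 20 at progression | – | −3.75 | −3.73 | −3.73 |
| last observed score; QOL falls 10 at progression | 0.6 | −5.53 | −2.42 | −1.96 |

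**4. Reading the table.** The direction comes from selection. At strength 0.6 on observed scores, independence GEE overstates the control mean by 10.05 points and the SBRT mean by 10.05 − 3.77 = 6.28.

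The share of the independence-GEE bias that the likelihood model keeps is:

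- current unobserved score: 1.11/2.67 = 42%, 2.29/4.68 = 49%, 3.72/5.85 = 64%;
- latent slope: 82% to 84%;
- a fall at progression only: 99%.

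In these rows exchangeable GEE is within 0.5 points of the likelihood model.

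**The case against.** Several points on the other side stand.

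- QOL is a secondary endpoint and section 17.4 says differences will be explored.
- The plan does not say that GEE will be unweighted. An exchangeable working correlation removes most of the problem when dropout follows observed scores.
- The two model sentences need not conflict: GEE is a repeated-measures method, and the second sentence can be read as specifying the first.
- That collection stops at progression is an inference from three sections.
- The documents do not say that progression follows declining QOL. Section 15.1.2 defines progression by imaging. Section 7.4 does admit clinical criteria such as cachexia, and sections 2.2 and 6.2.1 link progression with pain, vomiting, anorexia and weight loss. The dependence is plausible but not established.

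Two stronger readings are tempting and not supported. A reader might infer that a mixed model cures the problem. That holds only if dropout depends on scores already observed. Here the loss is caused by progression, after which no QOL is collected, and the last nine rows of the table show what remains. A reader might also reach a larger bias, such as 6 to 11 points for independence GEE, by assuming that dropout depends on scores more steeply in the control arm and that 36–40% against 63–67% still report at 12 months. Nothing in the documents supports an arm-specific dependence, since a higher progression rate is a different matter, and the design medians give 25% against 44%.

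**Conclusion.** The point holds as a gap in specification with a risk of bias, not as a demonstrated bias. Unequal loss between arms follows from the design's own medians. Whether it biases the QOL comparison, and by how much, depends on the dropout mechanism and on GEE details that the plan leaves open.

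If dropout follows observed scores, the illustrative 12-month bias is about 2 to 5 points against SBRT for independence GEE, under 1 point for exchangeable GEE and near zero for a likelihood model. If dropout follows unobserved decline, or QOL falls at progression, the likelihood model keeps about half to all of the independence-GEE bias (42% to 99% in the runs with one such mechanism) and is about the same as exchangeable GEE. If dropout is unrelated to QOL and QOL does not fall at progression, there is essentially no bias.

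The point sizes rest on the assumed variances and dropout strengths. They also take QOL regardless of progression as the target; a target of QOL while progression-free would change what counts as bias. The PFS conclusion is not affected, so this is a minor but cheap improvement.

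**What to change.** In section 17.4, replace the GEE sentence as it applies to QOL with one named analysis: a likelihood-based mixed model for repeated measures with baseline score, visit and visit-by-arm, using all observed scores. Weighted GEE is an acceptable alternative.

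State in the same place:

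- that the analysis assumes dropout depends only on observed data;
- whether the target is QOL while progression-free or regardless of progression, and how death is handled;
- a sensitivity analysis for informative dropout, such as a delta-adjusted or pattern-mixture analysis.

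A sentence in section 7.5 or a footnote in section 14 should say whether questionnaires stop at progression.

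The cost is wording and a little more analysis work, with no extra data. If the sponsor chooses the target regardless of progression, scores after progression would be extrapolated unless questionnaires continue. Continuing them would be a separate protocol change with its own burden.

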17.4.1 Stratification

We will stratify by ECOG performance status (0 and 1 vs 2).

17.5 Stopping Guidelines

17.5.1 Toxicity Monitoring

Adverse events or toxicities will be monitored throughout the study and follow-up periods with Grade 4 and higher events reported to Stanford promptly, as outlined in Section 11. Toxicities, Adverse Events, and Reporting Requirements. Grade 3 and lower adverse events will be recorded on AE logs at each institution and reported to Stanford as requested (See Section 11.2.3). An interim review of toxicities between the two arms will be conducted by all co-investigators when 16 evaluable patients have been enrolled. If there is a >20% increase in G3 or higher toxicities in the treatment arm compared with to the control arm, then we will revise the protocol as appropriate.

In our recently completed Phase II study using 33Gy in 5 fractions, there were no Grade 5 toxicities and the Grade 3-4 toxicity rate attributable to SBRT was 8%. For this study, we would expect the observed rate of grade 3 or higher toxicities with the first 6 months to be slightly higher due to the toxicity related to Folfirinox and to the expansion to additional sites; however, we expect the overall rate to be less than 12%. A toxicity level of 20% would be considered the upper boundary.

We have developed a continuous Bayesian stopping guideline with a prior distribution of Beta (6, 44), representing a toxicity rate of 15% (just above our expected rate). The guidelines will recommend that the therapy be re-evaluated if the posterior probability that the toxicity rate exceeds the 20% boundary is greater than 65%. Once an initial cohort of 10 participants has been enrolled and followed for 6 months, toxicity will be monitored continuously. Table 1 below summarizes the stopping guideline boundaries for SBRT related events.

Table 1

Cohort size	Observed number of toxicities that trigger re-evaluation
11-14	5
15-20	6
21-27	7
28-33	8
34-39	9
40-46	10
47-52	11
53-58	12
59-65	13
66-71	14
72-78	15
79-84	16
85-86	17

The probability of triggering the stopping guidelines was assessed for a range of underlying toxicity rates based upon simulations with 5000 replicates (Table 2). In the expected range of toxicity, the probability of stopping to re-evaluate was less than 5% if the underlying toxicity was 10%; whereas the probability of stopping to re-evaluate for unacceptable levels was 74.2% or higher.

Table 2

True underlying toxicity rate	Probability of triggering stopping guideline boundaries
1%	0%
5%	0.1%
8%	1.4%
10%	4.2%
12%	11.3%
15%	31.2%
20%	74.2%
25%	95.7%

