Adverse events will be tabulated by type and grade at each follow-up. All adverse events will be reported to the Data Safety and Monitoring Board (DSMB), GI Clinical Research Groups (CRG) if applicable, and each institution's IRB, as well as to Stanford as the Coordinating Center according to the guidelines set forth in this protocol. The expected toxicity rate is 12% or less and a continuous Bayesian stopping guideline has been developed (see section 17.5.1, p 64) representing the 12% toxicity rate. The study may be stopped before reaching the accrual goal at the recommendation of any of these groups based upon stopping guidelines for toxicity as described below.

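### The written toxicity rule (20% boundary) does not produce Tables 1 and 2, which fit a 15% boundary; as written it flags a true 20% rate about 11% of the time, not 74.2%

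*Combined protocol and SAP*

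**What the plan says.** Section 17.5.1 (Toxicity Monitoring) defines a continuous Bayesian guideline in four parts.

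- Prior: "a prior distribution of Beta (6, 44), representing a toxicity rate of 15% (just above our expected rate").
- Reference rate: "A toxicity level of 20% would be considered the upper boundary".
- Trigger: therapy is to be re-evaluated "if the posterior probability that the toxicity rate exceeds the 20% boundary is greater than 65" per cent.
- Timing: "Once an initial cohort of 10 participants has been enrolled and followed for 6 months, toxicity will be monitored continuously".

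Table 1 is then offered as the result: "Table 1 below summarizes the stopping guideline boundaries for SBRT related events". It runs from 5 events at cohort sizes 11 to 14 up to 17 events at 85 to 86. Table 2 gives trigger probabilities from 5000 simulated trials: 4.2% at a true rate of 10%, 74.2% at 20% and 95.7% at 25%. The text summarises the upper end as "probability of stopping to re-evaluate for unacceptable levels was 74.2% or higher".

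Section 17.4 (Plan of Analysis) describes the same guideline differently, as "representing the 12% toxicity rate".

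**The concern.** Prior, boundary and posterior threshold are all given, so they fix the trigger count at every cohort size. The printed counts look far too low for a 20% boundary. Five events in 11 patients sounds alarming, but the prior carries the weight of 50 patients at a mean of 12%, and those data do not lift the probability of exceeding 20% anywhere near 65%.

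If sentence and tables are different rules, the trial has two continuous toxicity rules with very different sensitivity. A statistician who programs the sentence gets a rule without the performance shown in Table 2. A committee that reads Table 1 is not applying the 20% criterion it was told about. Section 17.4 lets several bodies recommend stopping on this guideline, so two of them could reach opposite conclusions from the same data.

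**Working it through.** **Inputs.** From section 17.5.1: prior Beta(6,44), boundary 20%, posterior threshold 0.65, first cohort of 10 and then continuous monitoring, Table 1 covering n = 11 to 86, Table 2 from 5000 replicates. From section 17.3.2: 86 patients per arm, which matches the last row of Table 1.

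**Formula.** With x toxicities in n patients the posterior is Beta(6 + x, 44 + n − x). The trigger at n is the smallest x with P(p > b | Beta(6 + x, 44 + n − x)) > 0.65, where b is the boundary. Trigger probabilities are exact: the binomial path is followed patient by patient, and the probability of first reaching the trigger is summed over n = 11 to 86.

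**Step 1: does Table 1 give Table 2?** Yes. The largest gap is 0.7 percentage points. The simulation standard error at 74.2% is √(0.742 × 0.258 / 5000) = 0.6 points.

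**Step 2: does the written rule (b = 20%) give Table 1?** No, at none of the 76 cohort sizes.

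| n | Trigger, b = 20% | Table 1 | Trigger, b = 15% |
|---|---|---|---|
| 11 | 8 | 5 | 5 |
| 14 | 9 | 5 | 5 |
| 20 | 10 | 6 | 6 |
| 40 | 14 | 10 | 10 |
| 86 | 24 | 17 | 17 |

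At n = 11 with x = 5 the posterior is Beta(11, 50), and P(p > 20%) = 0.323. With x = 7 it is 0.576 and with x = 8 it is 0.694, so the written rule first triggers at 8. At n = 86 with x = 17, P(p > 20%) = 0.167; the rule first triggers at x = 24 (0.710, against 0.634 at x = 23). Across the whole of Table 1 the posterior probability of exceeding 20% at the printed trigger lies between 0.13 and 0.35.

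**Step 3: which rule does give Table 1?** Keep the prior and the 0.65 threshold and set b = 15%. All 76 entries then match. P(p > 15%) is 0.65 to 0.76 at every printed trigger, and at one event fewer it is at most 0.647.

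**Step 4: trigger probabilities, maximum cohort 86.**

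| True rate | Table 2 (stated) | Table 1, exact | Rule as written, exact |
|---|---|---|---|
| 8% | 1.4% | 1.3% | 0.0% |
| 10% | 4.2% | 4.4% | 0.01% |
| 12% | 11.3% | 11.6% | 0.1% |
| 15% | 31.2% | 31.9% | 0.9% |
| 20% | 74.2% | 74.0% | 11.4% |
| 25% | 95.7% | 95.2% | 44.6% |

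At a true rate of 20% the ratio is 74.0 / 11.4 = 6.5.

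**Step 5: can another reading rescue the sentence?**

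- First look at n = 1, 10 or 11: still 11.4% at a true 20%.
- Monitoring continued to 172 patients: 23.0% at a true 20%.
- A prior whose mean really is 15%, namely Beta(7.5, 42.5), Beta(6, 34) or Beta(9, 51), with b = 20%: all 76 entries still disagree, and the trigger probability at a true 20% is 18% to 30%.
- b = 20% with Beta(6,44) and the threshold varied from 0.02 to 0.89: the best value, 0.17, still misses 34 of 76 entries.
- b = 12% with Beta(6,44) and threshold 0.65: all 76 disagree.

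**Step 6: the prior.** The mean of Beta(6,44) is 6 / (6 + 44) = 12%. That equals the upper end of the expected rate in section 17.5.1 and the figure in section 17.4. It is not 15%.

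**The case against.** The strongest reply is that sites and committee have explicit integer triggers. Anyone who monitors from Table 1 gets the performance shown in Table 2, so the 11% figure arises only if someone sets the table aside and programs the sentence. This stands: the printed triggers are the more sensitive rule, and harm is not inevitable. But the plan presents the sentence as the definition and the table as its summary, so following the sentence is a legitimate reading.

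A second reply is that two labels were probably misplaced: 15% was the posterior boundary, and 20% the unacceptable rate at which performance was assessed. That would explain every number, but no passage says so, and it is for the sponsor to confirm.

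Third, other safeguards exist: a review of toxicity by arm at 16 evaluable patients, 24-hour reporting of serious events of grade 3 and above, calls every other month and yearly outcome review. The guideline also recommends re-evaluation and does not halt the trial. All true, but none of these is a continuous rule with stated operating characteristics, and none settles which of the two rules applies.

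**Conclusion.** The concern holds. The sentence in section 17.5.1 and its two tables are different rules. The match to a 15% boundary is exact for Table 1 and within simulation error for Table 2. The size of the discrepancy is 3 events at 11 patients rising to 7 at 86, and a trigger probability at the stated upper limit of 20% of 11.4% in place of 74.2%. The 11.4% assumes independent patients, a look after each one, and a maximum monitored cohort of 86. The last is supported by the end of Table 1, its restriction to SBRT-related events and the size of one arm. The description of the prior as 15% is a separate error in the same paragraph. The calculation shows which boundary generated the tables, not which boundary the trial should use.

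**What to change.** State one rule in section 17.5.1 and make the sentence, Table 1 and Table 2 follow from it.

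- If the tables are kept, the sentence must give the 15% boundary that generates them, and 20% can remain only as the rate at which performance is reported.
- If the 20% sentence is kept, replace Table 1 with the triggers it implies (8 at 11 patients up to 24 at 86), restate Table 2 (about 11% at a true 20% and 45% at 25%), and withdraw the claim of at least 74.2%.

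In either case describe Beta(6,44) as having a mean of 12%. Section 17.4 already uses 12% and needs no new number, only wording that separates the prior mean from the boundary. Which boundary is intended is for the sponsor and the DSMC to decide. Whichever is chosen, anyone already monitoring should confirm which rule they have been applying. The cost is a text or table correction, with no additional patients or data.

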Another phase II study treated locally advanced pancreatic cancer patients with gemcitabine followed by 25 Gy of SBRT delivered with Cyberknife and maintenance gemcitabine chemotherapy. In this study, the excellent progression free survival was confirmed from previous studies (81%). The median overall survival was 11.4 months, median time to progression was 9.7 months and 1 year survival was 50%(14). There were no significant acute GI toxicities however, of the 15 patients alive >6 months after SBRT, 7 (47%) experienced Grade 2 or greater GI toxicity, with 2 (13%) of the 15 experiencing Grade 3 or greater GI toxicity.

More recently, another phase II study of 25 Gy in a single fraction using a linac-based approach (Trilogy™, Varian Medical Systems, Palo Alto, CA) integrated with gemcitabine chemotherapy resulted in a 50% overall survival at 1 year and a 94% freedom from local progression at 1 year. Four patients (15%) developed Grade 2 ulcers and 1 patient (5%) developed a duodenal perforation (Schellenberg et al, IJROBP 2011).

Recently, we completed a multi-center phase II trial demonstrating the efficacy of SBRT (33

Gy in 5 fractions) in combination with gemcitabine chemotherapy. No significant toxicities were observed and median overall survival was 18 months. These data compare favorably to other studies reported in the literature. Based upon these promising data, we hypothesize that adding SBRT to a more aggressive systemic chemotherapy (FOLFIRINOX), will result in further improvement in OS in patients with locally advanced pancreatic cancer.

The proposed randomized study is a logical extension of the previously reported studies and will establish the efficacy of adding SBRT to FOLFIRINOX chemotherapy. Our prior multi-center phase II experience demonstrated the feasibility and efficacy of this approach in patients with locally advanced pancreatic cancer.

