17.3.3 Criteria for Future Studies

We anticipate that fractionated SBRT with IGRT based linac systems will result in similar progression free survival at one year (80-90%) to single fraction SBRT but with a (20%) decrease in late gastrointestinal toxicity at one year. The current patient population will serve as a comparator for the future trials in terms of time to progression and provide additional information with regards to radiation treatment planning.

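### Scheduled adverse-event evaluation stops at progression or surgery, inside the 6-month toxicity window and the 3-month GI window, so the SBRT toxicity boundary can under-trigger

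*Combined protocol and SAP*

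**What the plan says.** **The windows.** Section 17.5.1 states its expected rate of grade 3 or higher toxicity for the first 6 months and sets 20% as the upper boundary. Table 1 gives the event counts that trigger re-evaluation for SBRT-related events, for cohorts of 11 to 86. The start is described so: "Once an initial cohort of 10 participants has been enrolled and followed for 6 months, toxicity will be monitored continuously". The acute GI endpoint in 17.1.2 counts selected grade 2 or higher events, and other grade 3-4 GI toxicity, within 3 months of treatment.

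**When AEs are evaluated.** Section 11.3 and the Study Calendar place AE evaluation at mFFX cycles and follow-up visits. On visits, 7.2 says: "Patients will have consultations in the first year every three months following study treatment".

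**When that ends.** Section 7.4: "Patients will remain enrolled on this protocol until there is evidence that their disease has progressed either locally or distantly". Section 7.5 lists progression, and resectability followed by surgery, among the reasons for removal, and adds: "Patients withdrawn from the study will be followed for overall survival only". Section 7.2 says the same of surgery. Its sentence on years 2 and 3 runs visits "until death or study withdrawal (due to progression, patient withdrawal, or noncompliance".

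**What points the other way.** Section 17.5.1 opens by saying that toxicities are watched over the study and its follow-up. Section 11.1.1 asks for grade 3 and higher SAEs within 24 hours and sets no cut-off at progression.

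**The concern.** A site that follows 7.4 and 7.5 has no scheduled AE evaluation left for an irradiated patient who progresses at month 2 or goes to surgery at month 4. The guideline still needs that patient's toxicity status at 6 months, and the GI endpoint needs it at 3 months.

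The two statements that point the other way close only part of the gap. The follow-up named in 17.5.1 is the follow-up that 7.4 and 7.5 end. SAE reporting covers serious events that a site happens to learn of. Non-serious grade 3 events go onto AE logs, and the grade 2 GI events in the endpoint normally have no expedited route, so both depend on the visits that stop.

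At stake is the formal safety boundary for SBRT. Table 2 advertises its operating characteristics on the footing that every patient's outcome is known.

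**Working it through.** **Inputs.** SBRT-arm median PFS 10.2 months, exponential, 86 patients (17.3.2); boundaries from Table 1 and trigger probabilities from Table 2 (17.5.1). PFS is timed from randomization. Under an exponential model the same shares apply from SBRT onward for patients progression-free at that point.

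**Step 1: reproduce Table 2.** An exact binomial recursion over Table 1, checking after each patient from 11 to 86 with all toxicity observed, gives:

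| True rate | Computed | Printed |
|---|---|---|
| 10% | 4.4% | 4.2% |
| 12% | 11.6% | 11.3% |
| 15% | 31.9% | 31.2% |
| 20% | 73.9% | 74.2% |
| 25% | 95.2% | 95.7% |

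The printed figures therefore correspond to complete observation of up to 86 patients.

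**Step 2: share with a PFS event inside each window.** S(t) = 2^(-t/10.2).
- 3 months: 1 - S(3) = 0.184, about 16 of 86.
- 6 months: 1 - S(6) = 0.335, about 29 of 86.

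Both include deaths, which leave no later toxicity to miss.

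**Step 3: share of toxicities seen if none is captured after progression.** This is the mean of S over the onset distribution. Onset is taken as independent of progression. The onset shapes are assumptions, because the plan gives none.
- Uniform over 0-6 months: [10.2/(6 ln 2)] x 0.335 = 0.821.
- Uniform over 3-6 months: [10.2/(3 ln 2)] x (0.816 - 0.665) = 0.738.
- Early, Beta(1,3) on the 6-month scale: 0.906.

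**Step 4: feed 20% x share through the Step 1 recursion**, keeping every patient in the denominator.

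| Capture after progression | Onset | Rate seen | Chance of crossing |
|---|---|---|---|
| Complete | any | 20.0% | 74% |
| None | early | 18.1% | 59% |
| None | uniform | 16.4% | 44% |
| None | months 3-6 | 14.8% | 30% |
| Half | uniform | 18.2% | 60% |
| Half | months 3-6 | 17.4% | 53% |
| Progression found only at 3-monthly visits, AEs assessed there | early | 19.5% | 71% |
| Same | uniform | 18.2% | 60% |
| Same | months 3-6 | 16.3% | 43% |

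In the visit-based rows, all events before month 3 are seen and later ones only if there is no PFS event by month 3. For uniform onset the share is 0.5 + 0.5 x 0.816 = 0.908; for early onset, 0.875 + 0.125 x 0.816 = 0.977; for months 3-6, 0.816. With no capture and uniform onset, a true 25% rate crosses 77% of the time instead of 95%.

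**Step 5: the other denominator rule.** If incomplete patients are dropped, about 86 x 0.665 = 57 remain. The recursion stopped at 57 crosses 59% of the time at a true 20% rate.

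**The case against.** The strongest reply is that the plan nowhere says an early progressor counts as toxicity-free. Section 17.5.1 speaks of participants followed for 6 months and elsewhere of evaluable patients; 15.1.1 refers to evaluability for toxicity. Many SBRT-related grade 3 or higher events would also be SAEs, and progression will often be found at an imaging visit where AEs are assessed anyway. All of this stands. It makes the loss conditional, and with early onset and visit-detected progression it is nearly nil (71% against 74%). It does not supply the missing rule, and less favourable combinations cost considerably more.

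Other readings may tempt a reader but are not supported:

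- **That a third of patients have a truncated window for both measures.** The 33% belongs to the 6-month window only. The 3-month share is 18%, and a truncated window is not a lost event: on average 82% of the 6 months is still observed.
- **That the background shows the guideline will miss late toxicity.** Section 2.2 reports that "of the 15 patients alive >6 months after SBRT, 7 (47%) experienced Grade 2 or greater GI toxicity". That study gave 25 Gy in a single fraction, the 47% is grade 2 or higher, no onset dates are given, and events after 6 months lie outside the guideline's window.
- **That toxicity after 3 months goes unreported.** Section 17.3.3 anticipates a "decrease in late gastrointestinal toxicity at one year", but it is a passage about future studies. Section 17.4 already tabulates AEs at each follow-up, and the calendar schedules AE evaluation at 6, 9 and 12 months. A separate late-toxicity analysis would be a preference.
- **That unequal truncation flatters SBRT.** At the control median of 6 months, 50% have a PFS event by 6 months against 33% with SBRT. More loss in the control arm makes SBRT look relatively worse, which is the cautious direction.

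Separately, Table 1 does not follow from the written rule: Beta(6,44) with a 20% boundary and 65% probability needs 8 events at n = 11 and 24 at n = 86, against the printed 5 and 17. Text and table need reconciling. The 74% used here comes from the printed table, and the mismatch does not restore missing follow-up.

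**Conclusion.** The concern holds in a conditional form. Scheduled AE evaluation ends at progression or surgery while both safety measures run on fixed windows, and the plan does not say how a patient with an incomplete window counts. The shares affected, 33% at 6 months and 18% at 3 months including deaths, follow from the plan's own PFS assumption.

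A reader might infer that the boundary does under-trigger. The documents support only that it can. The fall from 74% to about 44% (30% to 59% by assumed onset) needs two things the plan does not state: no capture after progression, and early progressors kept in the denominator as toxicity-free. Half capture or visit-detected progression gives about 60% to 71% with uniform or early onset, and 43% to 53% if onset is confined to months 3 to 6. Dropping incomplete patients gives 59%. Table 2 can be relied on only if the windows are observed in full, and nothing in the plan secures that.

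**What to change.** In 7.4, 7.5 and the Study Calendar, state that AE evaluation continues through the 3- and 6-month windows in every randomized patient, regardless of progression, surgery or protocol withdrawal, and ends only at death or withdrawal of consent. A telephone call or local records would suffice. Amend the survival-only sentence in 7.5 to match.

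In 17.5.1, start the 6-month clock at SBRT for the guideline. Count a patient in the Table 1 cohort only when the window is complete or an event has occurred, and say how deaths and withdrawn consent within the window are treated. In 17.1.2, name the start of the 3-month window in each arm.

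**Cost.** Protocol wording, and a few extra calls to patients already followed for survival. Events after progression may be due to disease or next-line therapy; the attribution columns for FFX and SBRT on the AE form partly address this. Counting events at once but event-free patients only after 6 months makes the running rate lean high during accrual, so any error is towards earlier re-evaluation.
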